11. ETHICS

The study will be performed in accordance with the protocol, with the latest version of the Declaration of Helsinki, with Good Clinical Practice (ICH-GCP E6(R2) and applicable regulatory requirements.

11.1. Ethics committee

The final study protocol, including the final version of the Informed Consent Form and other information given to subjects e.g. advertisements, must be approved or given a favourable opinion in writing by an Ethics Committee (EC) as appropriate. The Principal Investigator is responsible for informing the EC of any amendment to the protocol, in accordance with local requirements. Progress reports and notifications of any serious and unexpected adverse drug reactions will be provided to the EC according to local regulations and guidelines.

11.2. Informed consent

The Principal Investigator at each centre will ensure that the subject is given full and adequate oral and written information about the nature, purpose and possible risks and benefits of the study. Subjects must also be notified that they are free to discontinue from the study at any time. The subject should be given the opportunity to ask questions and allowed time to consider the information provided.

The subject's signed and dated informed consent must be obtained before conducting any procedure specifically for the study. The monitor(s), the auditor(s), and the CA(s) will be granted direct access to the subject's original medical records for verification of clinical trial procedures and/or data, without violating the confidentiality of the subject, to the extent permitted by the applicable laws and regulations and that, by signing a written informed consent form, the subject or the subject's legally acceptable representative is authorizing such access.

The original signed Informed Consent Form (ICF) must be stored in the Investigator's Study File. A copy of the signed ICF must be given to the subject.

The EC must approve modifications that lead to a revised ICF before the revised form is used.

11.3. Subject data protection

The ICF will incorporate wording that complies with relevant data protection and privacy legislation. Pursuant to this wording, subjects will authorize the collection, use and disclosure of their study data by the investigator and by those persons who need that information for the purposes of the study.

The ICF will explain that study data will be stored in a computer database, maintaining confidentiality in accordance with national data legislation. All data computer processed by the sponsor will be identified by ImpresU WP3/Subject ID/Initials.

The ICF will also explain that for data verification purposes, authorized representatives of the sponsor, a regulatory authority or an EC may require direct access to parts of the hospital or practice records relevant to the study, including subjects' medical history.

11.4. Insurances

The Norwegian study subjects are covered by Legemiddelansvarsforsikringen.

The Swedish study subjects are covered by Svenska Läkemedelsförsäkringen, LFF Service AB.

The Dutch study subjects are covered by CNA Insurance Company (Europe) S.A.

The Polish study subjects are covered by Towarzystwo Ubezpieczeń i Reasekuracji „WARTA”.

12. PROTOCOL DEVIATIONS AND AMENDMENTS

Modifications to the signed protocol are only possible through approved protocol amendments and with the agreement of all responsible persons. Details of non-substantial amendments are to be clearly noted in the amended protocol.

A change that concerns; a new trial site, new principal investigator and or a new informed consent form should only be submitted to the concerned EC.

In case of a substantial protocol amendment (e.g. change of; main purpose of the trial, primary/secondary variable, measurement of primary variable, investigational product, or dosing), the concerned EC and CA must be informed and should be asked for its opinion/approval prior implementation of amended protocol, as to whether a full re-evaluation of the ethical aspects of the study is necessary by the committee. This will be fully documented.

The Investigator must not implement any deviation from, or change to the protocol, without discussion with, and agreement by the Sponsor and prior review and documented approval/favourable opinion of the amendment from the relevant EC and CA, except where it is necessary to eliminate an immediate hazard to study subjects, or where the change(s) involves only logistical or administrative aspects of the study (e.g. change in monitor(s), change of telephone numbers).

13. REPORT AND PUBLICATIONS

After completion of the study, the results will be analysed and a clinical study report will be prepared. Within one year after the end of the study, the sponsor will submit a study report with the results of the study, including any publications/abstracts of the study, to the accredited EC and the CA. In addition, upon study completion and finalization of the study report the results of this trial will be either submitted for publication and/or posted in a publicly accessible database of clinical trial results.

14. STUDY TIMETABLE

14.1. Study Period

Subject enrolment is estimated to start by November 1st 2019, subject enrolment is estimated to stop on December 31st of 2020 and last subject last visit is estimated to be on December 31st 2021.

14.2. Definition of “End of study”

Data collection will stop when the target number of participants are included. The study ends when the last follow up is made for all included participants. Hence, the study may formally end before results are accepted for publication. The sponsor will notify the concerned EC and the CA of the end of the study within a period of 90 days.

1. INTRODUCTION

1.1. Background

Recurrent urinary tract infection (UTI) in elderly women is a major driver of antibiotic prescription (1-9). Hence, the question of feasible and appropriate preventive measures are important issues in this field. Methenamine hippurate is frequently prescribed in Norway and Sweden as prophylaxis for recurrent UTI (9). Methenamine hippurate is hardly used outside of Scandinavia. Methenamine hippurate acts via the production of formaldehyde from hexamine, which in turn acts as a bacteriostatic agent, therefore methenamine hippurate is not defined as an antibiotic. According to a Cochrane review 2012 the rates of adverse events for preventing UTI was low (10). Although this review showed methenamine hippurate might be effective in preventing UTI in the short term, there is a need for large well-conducted randomised controlled trial (RCT) to clarify both the safety and effectiveness of preventive methenamine hippurate for longer term use (11-16). This is particularly important for longer term use for people without neuropathic bladder disorders (10). A Norwegian longitudinal observational study including women aged 50-80 years with recurrent UTI indicated a significant and large reduction of more than 50% in antibiotic prescriptions for UTI after start of prophylactic methenamine hippurate ([name], personal communication). This further strengthens the need for an RCT of methenamine hippurate as prophylaxis for recurrent UTI.

Escherichia coli (E. coli) is a part of the human gastrointestinal microbiota (17). Uropathogenic E.coli from fecal reservoirs are the predominant causative microbes in uncomplicated UTIs (18-20). Previous studies have shown that strains of E.coli can be divided into phylogenetic subgroups (A, B1, B2, C, D, E and F), and that subgroup B2 and D represents the most virulent types and are associated with extra-intestinal infections (21-23).

We aim to investigate whether the phylogenetic subgroups of E.coli present in the urine cultures at inclusion can have a modifying role on the preventive effect of Methenamine hippurate in this study. If feasible, we will also investigate whether or not subsequent episodes of acute UTIs in elderly women with recurrent UTI are caused by E.coli of the same phylotype.

1.2. Rationale for conducting this study

Existing knowledge suggests that methenamine hippurate is a safe drug with few and mild side effects and with the potential to significantly reduce antibiotic usage for women with recurrent UTIs. Methenamine hippurate has been on the market for a long time but has never been tested to prevent recurrent UTIs in larger RCTs with long time follow-up. Hence, this must be proven in a large randomised trial before recommending large scale use of this drug (10).

2. STUDY OBJECTIVES AND ENDPOINTS

The primary objective of this study is to investigate if taking methenamine hippurate reduce the need for antibiotic usage due to recurrent UTI (measured as number of antibiotic courses). The remaining objectives are considered secondary. Pyelonephritis, hospitalization and death will be registered as safety endpoints in the study.

Objectives		Outcome Measures / variables / endpoints	Time point(s) of evaluation of this outcome measure (if applicable)
Primary Objective			
1	The primary objective of this study is to investigate if taking methenamine hippurate reduces the need for antibiotic usage due to recurrent UTI (measured as number of antibiotic courses).	Number of UTI antibiotic treatments during the six months of treatment. If the participant receives >1 antibiotic course for UTI without symptom relief it is regarded as one episode and counted as one antibiotic treatment. If there has been an asymptomatic period of at least 14 days in-between two UTI antibiotic courses, this is regarded as a new antibiotic treatment.	After six months of treatment.
Secondary Objectives			
2a	To investigate if methenamine hippurate will have a prolonged effect on antibiotic usage even after discontinuation.	Number of UTI antibiotic treatments during the six months following completion of treatment. If the participant receives >1 antibiotic course for UTI without symptom relief it is regarded as one episode and counted as one antibiotic treatment. If there has been an asymptomatic period of at least 14 days in-between two UTI antibiotic courses, this is regarded as a new antibiotic treatment.	Six months after completing (12 months after commencing) treatment.
2b	To investigate if taking methenamine hippurate reduces the incidence of UTI.	Number of UTIs (acute symptoms specific/related to the urinary tract) during the six months of treatment. If the participant has had >1 UTI episode without symptom relief it is regarded as one episode. If there has been an asymptomatic period of at least 14 days in-between two UTI episodes, this is regarded as a new episode.	After six months of treatment.
2c	To investigate if methenamine hippurate can reduce severity of UTI symptoms.	Registration of symptom severity when initiating treatment for UTI.	After six months of treatment.
2d	To investigate if methenamine hippurate can reduce duration of UTI episodes.	Registration of number of days of symptoms during UTI episodes.	After six months of treatment.

2e	To investigate if number of complications such as pyelonephritis and hospital admission for UTI differ between methenamine hippurate and placebo.	Registration of number of pyelonephritis and hospital admission for UTI.	Six and 12 months after commencing treatment.
2f	To investigate if phylogenetic subgroups of E. coli found at inclusion is an effect modifier in the above outcomes.	(see above)	(see above)

[figure not shown]
3. STUDY DESIGN AND PROCEDURES

3.1. Overall study design and flow chart

Study design: Blinded randomised controlled phase IV trial where patients are randomised to active intervention (methenamine hippurate) or controls (placebo).

Setting and study population: Women aged ≥ 70 years with recurrent UTIs in primary care. A total of 400 patients will be randomized in this trial, with approximately 100 patients in each of the participating countries; Norway, Sweden, Poland and the Netherlands.

Diagram 1. Schematic diagram of procedures:

3.2. Description of study visits

Day(s)	Visit 1 Screening and randomisation	Telephone follow-up in case of acute UTI episode(s)	Telephone follow-up every 30 days in all patients	Telephone contact by end of treatment	Telephone contact by end of study
	1	2-360	2-180	180	360
Informed consent	X				
Demography, level of care	X				
Medical history	X				
Physical examination,	X				
Dipstick urinalysis and urine culture	X	X			
Inclusion/exclusion criteria	X				
Randomisation	X				
Patient Reported Outcome		X	X	X	X
Concomitant medication**	X				
Serious Adverse Events		X	X	X	X*

* In case of SAE present and not resolved by day 360, this will be followed until resolution.

** After visit 1 concomitant medication will only be registered in case of SAE, otherwise not.

4. STUDY MEASUREMENTS AND VARIABLES

- number of UTI antibiotic treatments (name of drug, dosage and duration) during day 2-360
- number of UTIs (acute symptoms specific/related to the urinary tract) during day 2-360
- registration of symptoms and severity when initiating treatment for UTI. This will be measured by a scale 0-6 (no symptoms to worst possible) for each of the three cardinal symptoms and general condition.
- registration of number of pyelonephritis and hospital admission for UTI
- laboratory tests at Visit 1: urine culture and dipstick urinalysis regarding pH, nitrite and leukocyte esterase
- laboratory tests ordered by the ordinary clinician in case of episodes of UTI during the study period (urinary dipsticks regarding nitrite and leukocyte esterase and urine culture)
- level of care: general practice, residential home care or nursing home
- SAEs, whereas relationship with IMP cannot be excluded.

4.1. Primary variable

(See section “2 Study Objectives and Endpoints”).

4.2. Secondary variable(s)

(See section “2 Study Objectives and Endpoints”).

Statistical Analysis Plan (SAP)	Study code: ImpresU WP3 (Improving rational prescribing for UTI in frail elderly Work Package 3)
	Version No: Version 1.0
	Date: 9th of June 2023

4.3. Safety variable(s)

Pyelonephritis, hospitalization and death will be registered as safety endpoints. Methenamine hippurate has a well-documented safety profile and is a commonly used medication in primary care settings in Scandinavia. Therefore, non-serious adverse events (AE) will not be recorded in this study. All SAEs, whereas relationship with IMP cannot be excluded, occurring during the study period are recorded and reported according to guidelines in each country.

5. STATISTICS

5.1. Statistical analysis

It is the intention to adjust all analysis for the following confounding variables obtained at visit 1

- patient's age
- urine acidity (pH)
- number of antibiotic courses for UTIs in the 12 months preceding inclusion in the study
- presence of urease/stone-producing bacteria in urine culture day 1 such as *proteus*, some *klebsiella* species, *Morganella morganii*, *Corynebacterium urealyticum* and *providencia*
- use of local oestrogen
- patient has diabetes mellitus
- obesity defines as BMI ≥ 30
- presence of known mild abnormality of the urogenital tract
- if the patient is sexually active.
- If the patient previously have experienced urinary tract stone

Phylogenetic subtype of pure cultures of *E.coli* in the urine culture at inclusion will be analysed in a separate analysis if the number of cultures available for typing are not too small.

The statistical calculation relates to the study objectives described in section “2 Study Objectives and Endpoints”:

- 1 Negative binomial multivariable regression will be used where number of UTI antibiotic treatments will be the dependent variable. Group allocation together with the confounding variables above will be independent variables. Histograms of the dependent variable will determine if we need to adjust for zero inflation (or any other inflation).
- 2a Will be analysed using the same statistical approach as objective 1 above.
- 2b Will be analysed using the same statistical approach as objective 1 above. Number of UTIs will be the dependent variable.
- 2c The outcome variable is measured at first day of a UTI using a six grade ordinal scale. The median value from all UTIs will be used if the patient has more than one episode of UTI. Data will be analysed using ordinal multivariable logistic regression.
- 2d Will be analysed using the same statistical approach as objective 1 above. Number of days with symptoms will be the dependent variable. The median value from all UTIs will be used if the patient has more than one episode of UTI.
- 2e Will be analysed using the same statistical approach as objective 1 above. Number of severe events such as pyelonephritis or hospital admission will be the dependent variable.
- 2f Phylogenetic subgroup of pure cultures of *E.coli* in the inclusion urine culture will be analysed in a separate statistical analysis as an independent variable. We will add also an interaction term between phylogenetic subgroup and group allocation. All statistical analyses above will

Statistical Analysis Plan (SAP)	Study code: ImpresU WP3 (Improving rational prescribing for UTI in frail elderly Work Package 3)
	Version No: Version 1.0
	Date: 9th of June 2023

be redone adding phylotype and the interaction term as extra independent variables. (skriv om indelning av fylotyper). Only a limited number of independent variables will be included due to the lower number of observations. These will be determined by choosing the most statistically significant independent variables used in the prior regressions. The minimal model allowed will contain the following independent variables: group allocation, phylogenetic subgroup and their interaction term. The latter require at least 30 observations. A fourth independent variable will be added if there are at least 40 observations and so on.

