If the patient presents with symptoms of an acute UTI or are on antibiotic treatment for a UTI at the inclusion visit, the infection is handled by regular health services (GP or out of Hours (OOH) service). The patient will wait until 2 weeks after finishing treatment for the UTI before the researcher completes the inclusion and takes the baseline urine sample. The treatment with IMP will start the day after the completed inclusion of the patient. The current UTI should be registered at the baseline form as a UTI prior to inclusion in the study. The same procedure will be followed if the patient is on prophylactic treatment with UTI antibiotics, but is willing to stop the prophylactic treatment to enter the study. A note of the actions taken will be written in the comments section in the baseline CRF by the responsible researcher.

All data related to inclusion visit including trial name, study-ID and informed consent will be documented in the medical record of the patient.

Telephone follow-up in case of acute UTI episode(s)

Any episodes of acute UTI during the follow-up period (day 2-360) will be handled by regular health services (GP or out of Hours (OOH) service). Participants are informed at inclusion (Visit 1) to contact the trial team in case of any UTI-related health care contacts during the follow-up period. The study team will follow up each UTI episode until resolved with registration of relevant data by telephone contact and by ordering copies of medical records regarding the UTI episode including laboratory results regarding urinary dipsticks and urine culture.

Following data will be collected in case of acute UTI episode(s) during day 2-360 (telephone follow-up and from medical record):

- confirmation and registration of UTI symptoms (acute symptoms specific/related to the urinary tract), registration of symptom severity when initiating treatment for UTI. This will be measured by a scale 0-6 (no symptoms to worst possible) for each of the three cardinal

symptoms and general condition, Patient Reported Outcome (PRO) – grading of symptoms, see appendix

- UTI antibiotic treatment (name of drug, dosage and duration)
- registration of any pyelonephritis and hospital admission for UTI
- ordering copies of medical records regarding the UTI episode including laboratory tests performed by regular health service (dipstick urinalysis regarding nitrite and leukocyte esterase and urine culture)

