4.3. Subject enrolment and randomization

Included participants will be randomised strictly sequentially, as subjects are eligible for randomisation. If a subject discontinues from the study, the subject number will not be re-used, and the subject will not be allowed to re-enter the study.

Four sets of 100 random numbers each, one for each participating country, will be created using Research Randomizer. A block randomisation will be performed (the block size is concealed to prevent functional unblinding). The outcome will be transferred to a separate Excel spreadsheet for each country where each row, representing one patient, is sequentially numbered. Norway will have the numbers 1-100, Sweden 101-200, the Netherlands 201-300 and Poland 301-400. Each country will follow their randomisation list strictly sequentially. The inclusion will stop when a total of 400 participants are included in the study.

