8. STATISTICS

8.1. Sample size calculation

The sample size calculation is made for the primary objective described in section “2 Study Objectives and Endpoints”.

- We assume these selected older individuals will have an average of two courses of antibiotics for suspected UTI every six months (4).
- We assume a 25% reduction of antibiotic prescriptions during the first six-month period after introduction of methenamine hippurate. Hence the intervention group would have an average of 1.5 while the control group is assumed to remain around 2.0. We assume the standard deviation in each group to be 1.5. This will result in an effect size of 0.33 (small effect). We decided a smaller effect size would not be worth looking for.
- We assume the level of significance being 0.05, the power to be 0.80 and that a two tailed test is explored.
- We use Student's t-test as the statistical analysis but also calculate for Mann-Whitneys test (to be used if the outcome variable is not normally distributed). The planned statistical method to be used will be multivariate linear regression. Student's t-test and Mann-Whitneys test are used as surrogate methods to estimate sample size.

Under the assumptions given above an effective sample size of 286 patients (143+143) is required if t-test can be used. However, if Mann-Whitney's test is required we need 298 (149+149) patients. To achieve an effective sample size of at least 298 after considering a 25% loss to follow-up we aim to include at least 397 patients. We will aim to include 400 patients.

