6. REASONS FOR CHANGE FROM ORIGINAL PLANNING

During discussions within the research team we have decided to make some changes to the original statistical analysis plan described in the published study protocol:

- We changed the choice of regression model from standard linear regression to negative binomial regression since the dependent variable is an integer. However, all objectives and choice of independent variables remain unchanged.
- For objective 2c the number of scale steps is only 6 and we decided ordinal regression is a better method than standard linear regression on rank transformed data.
- The statistical analysis of objective 2f was previously described as being done if we had at least 60 observations. In further discussions we decided to clarify this as including as many independent variables as possible if the condition 10 observations for each independent variable is fulfilled. This gives a structure for how to choose independent variables.
- Imputation of data in intention to treat analysis was changed for patients dropping out after participating less than 3 months. We believe it would be a better representation to use the

average from similar patients remaining in the study rather than extrapolating data from a very short time frame.

- In the original study protocol (version 11.1) we first planned an intention to treat analysis as the main analysis, a complete case analysis as a secondary analysis and that a per protocol analysis would not be made. When the study protocol was published we decided to add that a per protocol analysis will also be made (26).

All decisions above were taken before data collection were completed and before any data were analysed.

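### Randomisation is blocked within four country lists, but no model includes country: a small loss of reported precision, with no bias in the primary rate ratio

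*SAP*

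**What the plan says.** Protocol 4.3 organises randomisation by country: "Four sets of 100 random numbers each, one for each participating country, will be created using Research Randomizer". The lists are blocked, with the block size concealed, and each country works through its own list in order. No other stratification factor is named. Patient numbers identify the country: 1–100 Norway, 101–200 Sweden, 201–300 the Netherlands, 301–400 Poland.

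SAP 5.1, like Protocol 8.2, opens its model specification with "It is the intention to adjust all analysis for the following confounding variables obtained at visit 1". The list has ten items: age, urine pH, antibiotic courses in the previous year, urease-producing bacteria, local oestrogen, diabetes, obesity, mild urogenital abnormality, sexual activity and previous urinary stone. Neither country nor site is there. Objectives 2a, 2b, 2d and 2e reuse the objective 1 model, the text for 2c and 2f does not name country, and no sensitivity analysis adds it. When the SAP moved from linear to negative binomial regression, section 6 confirmed the list: "However, all objectives and choice of independent variables remain unchanged".

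**The concern.** The primary outcome is a count of prescriptions, and prescribing is left to local care. Protocol 3.4 says: "Any episodes of acute UTI during the follow-up period (day 2-360) will be handled by regular health services". In this trial that means four national health systems, so antibiotic rates may well differ between countries.

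Blocking within country keeps the arms balanced on country, which makes the treatment estimate less variable when rates differ. A model without country does not recognise this. It treats the between-country spread as extra dispersion and reports a standard error larger than the estimate's real variability. Confidence intervals come out too wide, p-values too large and the type I error below 5%. The precision gained by stratifying is then not fully used.

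**Working it through.** **The plan's own figure.** Inputs from Protocol 8.1: mean courses over six months of 1.5 on active treatment and 2.0 on placebo (difference 0.5, rate ratio 0.75); a two-sided 5% level with 80% power; and, for the spread, "We assume the standard deviation in each group to be 1.5".

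- Normal approximation: n per arm = 2 × (1.96 + 0.842)² / (0.5/1.5)² = 141.3, so 142. The exact noncentral t gives 143, total 286, as stated.
- Mann-Whitney: 142 / (3/π) = 148.7, so 149 per arm, total 298, as stated.
- Loss to follow-up: 298 / 0.75 = 397.3, consistent with the stated 397 and the target of 400.

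**How much country spread the protocol's SD allows.** The control variance is 1.5² = 2.25. A Poisson count with mean 2.0 uses 2.0 of it. That leaves 0.25 for between-country variance and within-country dispersion together, so country can account for at most 0.25/2.25 = 11.1% of the outcome variance.

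For four equal-sized countries with evenly spaced rates, within-country dispersion = (0.25 − between-country variance) / mean squared rate:

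| Control rates | Between-country variance | Dispersion |
|---|---|---|
| equal | 0 | 0.25/4.00 = 0.0625 |
| 1.7–2.3 | 0.0500 | 0.2000/4.0500 = 0.0494 |
| 1.55–2.45 | 0.1125 | 0.1375/4.1125 = 0.0334 |
| 1.4–2.6 | 0.2000 | 0.0500/4.2000 = 0.0119 |

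**Simulation inside that limit.** 400 patients, 100 per country, blocks of 4 (assumed), rate ratio 0.75, 2400 runs, negative binomial fits with and without three country terms:

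| Control rates | SE excess without country | Power without | Power with |
|---|---|---|---|
| equal | 0.3% | 94.7% | 94.7% |
| 1.7–2.3 | 1.2% | 95.1% | 95.5% |
| 1.55–2.45 | 2.2% | 95.7% | 96.1% |
| 1.4–2.6 | 3.4% (0.0804 vs 0.0778) | 95.7% | 96.5% |

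In the widest case the simulated type I error was 4.0% without country and 5.0% with it. The log rate ratio with and without country differed by less than 0.001 in every case.

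A hand check of the widest case uses SE = √[(1/200)(1/2.0 + 1/1.5 + 2k)]. With k = 0.0625 (country left in the dispersion) this is 0.0804. With k = 0.0119 it is about 0.0772. The excess is about 4%, in line with the simulation.

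**With prior-year courses also in the model** (1000 runs; prior courses assumed Poisson at twice each patient's six-month rate, no entry selection), the last two excesses fall to 1.5% and 2.4%, and including country gains 0.2 to 0.8 points of power.

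**At the planned 298 evaluable patients.** In the two-means approximation with total SD 1.5 and a share ρ of variance between countries, the SE ratio is 1/√(1 − ρ):

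| ρ | SE excess | Power without | Power with |
|---|---|---|---|
| 1% | 0.5% | 82.2% | 82.4% |
| 5% | 2.6% | 82.7% | 83.9% |
| 10% | 5.4% | 83.3% | 85.8% |

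**Outside the protocol's SD.** With 298 patients, within-country dispersion 0.0625 and country spread added on top, multipliers of 0.6 to 1.4 give power of 83.9% without country and 87.6% with it. Multipliers of 0.4 to 1.8 give 78.0% and 86.6%. In these two cases the estimate's empirical SD is almost the same with and without country (0.0919 vs 0.0917; 0.0955 vs 0.0954), while the reported SE is not (0.0997 vs 0.0931; 0.1126 vs 0.0938). With 400 patients, rates of 1.0 to 3.25 and dispersion 0.3 (SD 2.03), the SE excess is 9.7% and power is 79.9% vs 85.5%. Adding prior courses, with entry restricted to at least three, brings this to 4.0% and 93.7% vs 95.6%.

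**The case against.** The omission itself is not in dispute; its importance is. The documents give no country rates, all countries share one entry threshold, and prior-year courses are already a covariate, so country may add little. The widest in-limit case gives country 0.20 of the 0.25 extra-Poisson variance, which leaves almost no heterogeneity between patients within a country. The 1.7–2.3 case is more moderate and costs 0.4 points of power. The error is conservative and does not favour the drug. All of this stands, and it limits the point to one of efficiency.

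Several technical objections also stand:

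- The drop in type I error to 4.0% should not be over-read. The Monte Carlo standard error at 2400 runs is √(0.05 × 0.95/2400), about 0.4 points, and a 3.4% SE excess by itself implies about 4.3%.
- Equal rates already show a 0.3% excess, so a small part of each figure is probably a fitting artefact.
- The other nine covariates were not simulated.
- The absence of bias applies to the log-link count models. In the ordinal logistic model for 2c, leaving out a prognostic factor can pull the odds ratio somewhat towards 1.
- 2c and 2d concern only patients who had a UTI, so the argument from stratified randomisation does not carry over to them directly. Country is useful there as an ordinary prognostic covariate.

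None of this is a reason to leave country out. It is the only stratum, it is never missing, and ten non-stratification variables are already adjusted for.

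**Conclusion.** The point holds. Country is the only randomisation stratum and is in no analysis model. The primary rate ratio is unaffected. What suffers is its reported standard error, interval and p-value, all in the conservative direction.

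Within the protocol's SD of 1.5 and with 400 patients, the standard error is 0.3% to 3.4% too large and the power loss is under one point. At 298 evaluable patients the two-means approximation gives a loss of up to about 2.5 points when 10% of the variance lies between countries. Losses of roughly 4 to 9 points arise only in scenarios that exceed the protocol's SD. These sizes rest on assumed country rates, equal country sizes and blocks of 4. The plan should be corrected because the correction costs almost nothing; validity is not at risk.

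**What to change.** Add country as a four-level fixed factor to the regressions for objectives 1 and 2a to 2d in SAP 5.1, and record the change in SAP 6. It should be specified before unblinding.

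For 2e, where events are probably sparse, add country with a fallback fixed in advance. One example is to omit country if the model does not converge or if a country has no events, since a sparse model can converge and still be unstable.

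For 2f, the SAP's rule of ten observations per variable applies: "A fourth independent variable will be added if there are at least 40 observations and so on". The minimal model plus country needs 40 observations if country counts as one variable, which matches how the SAP counts phylogenetic subgroup. It needs (3 + 3) × 10 = 60 if each country term is counted. The SAP should state which count applies.

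The cost is one line and three degrees of freedom. No data need to be collected, because country follows from the patient number. No patient is lost from the primary analysis set either, which SAP 5.1.1 restricts to patients with complete baseline data.
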